11. Subject Population: Describe the characteristics of the participant population including the inclusion and exclusion criteria and the number of participants you plan to recruit:

A total of 40 clients admitted to the Opioid Diversion Program (ODP) will be enrolled for the T-CAP study and all will receive the T-CAP intervention. Since the sample will be drawn from the existing ODP, sociodemographic characteristics are expected to be similar to census demographics for the corresponding communities, with approximately 59% male, 88% white, and average age of 32. In addition, we expect approximately 40% will need mental health services as part of their treatment and 60% will need services for medical problems. The ODP screens out individuals who have a criminal record of violent offenses. While all current ODP clients have a recent history (within the past 12 months) of opioid use or other substance use, we will confirm this during the RA's administration of the TCU Drug Screen 5 and TCU Drug Screen 5—Opioid Supplement. If this process reveals that the individual does not have a recent history of opioid or substance use, they will be offered the opportunity to remain in the study but excluded from the primary analyses. Furthermore, individuals who are not willing to consent to granting research staff permission to access their police and treatment services records, and individuals who do not understand the informed consent (see appendix for the Informed Consent Comprehension Questions), will be excluded from the study. Individuals must demonstrate the ability to speak and understand English and be at least 18 years old to participate in this study. At the Informed Consent meeting, the RA will determine that these criteria are met.

[figure not shown]
12. Recruitment Procedure: Describe your recruitment strategies including how the potential participants will be approached and precautions that will be taken to minimize the possibility of undue influence or coercion. Include copies of the recruitment letters, leaflets, etc. in your submission.

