The standing video call arrangements will be entered into the tracking spreadsheet by the Coach and uploaded to TCU Box. The Coach will then alert the RA that the spreadsheet is ready for download. The RA will download and proceed to set up the 6 remaining telehealth sessions in the app scheduling feature. The RA will send a confirmation text or email to the participant with the schedule. The day prior to each of the 6 telehealth calls, the app will generate an automated reminder message about the upcoming telehealth call. We anticipate that there will be changes to the video call schedules, and participants will be advised to contact the RA for any schedule changes on video calls.

T-CAP Intervention. Coaching will be provided to the total study sample (N=40) by two licensed substance use treatment counselors, currently available through the Lake County Health Department. The Coach position requires professional training as a substance abuse counselor or equivalent (e.g., counselor with mental health credentials). Each Coach will be responsible for 20 participants during the 11-month implementation period. The study calls for two half-time Coaches, one to cover responsibilities in the event that one Coach is not available (e.g., due to vacation). In the event that one or both Coaches are unable to continue the study, replacements will be engaged for the project [the IBR has a strong collaborative relationship with several behavioral service providers in Lake and Cook Counties in Illinois.] Each participant will be assigned to only one of the Coaches for the duration of the intervention.

The 12-week telehealth intervention features 7 video calls on a smart phone, that will connect the participant with a Coach who will deliver the 3 components of the intervention: brief Motivational Interviewing (MI) sessions (see Appendix for MI scripts), recovery support, and assertive referrals to services that are intended to augment ODP substance use treatment or during post-treatment when there is an additional treatment need during recovery, as identified by the participant.

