MI telehealth sessions are scripted; session 1 introduces the participant to MI, sessions 2-6 continue the dialog aimed at motivating the participant to identify issues and solutions, and session 7 focus is on continuing recovery with a plan. Coaches will keep brief case notes on paper versions of the MI scripts, and this information will be entered into the Coach Procedural Fidelity Checklist in Qualtrics . Coaches will use the information to prepare for the upcoming telehealth session. In addition, 10% of MI sessions will be audio-recorded for further evaluation of the fidelity to the MI script content. For each Coach, this is 7 MI sessions during the 11-month study window. MI sessions will be randomly selected for recording by the Project Coordinator, who will add an entry in the caseload tracking spreadsheet, flagging the video call MI portion to be recorded. This information will be provided to the Coaches in the caseload tracking spreadsheet that is downloaded by the Coaches from TCU Box-our secure file-sharing method. Coaches will be provided with hand-held recorders to capture only the MI portion of the video call. Coaches will upload the recordings to TCU Box, for download by the Project Coordinator. Coaches will delete the recording off the recorder. MI recording will be evaluated by only the PI and Project Coordinator, who is trained in MI. Downloaded files will be kept on the IBR secure server for the duration of the study. When the project is completed, the audio files will be destroyed. No MI fidelity recordings will be stored in TCU Box.

Scheduled Telehealth Sessions. Planned telehealth sessions (N=7) are front-loaded during the 12-week intervention, with 1 telehealth MI each week for the first four weeks, MI 5 in week 6, MI 6 in week 8, and MI 7 in week 12. The MI portion of each session is designed to be a brief 15 minute activity. In addition to MI, the Coach and participant will update on relapse concerns and recovery progress, and identified treatment needs for medical or additional behavioral healthcare treatment. The Coach will assist the participant with arranging services/appointments with an *assertive referral*, which involves the Coach providing the participant with treatment options and contacting a prospective provider on behalf of the participant to arrange for an appointment. To support the Coaches with

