resources to complete the assertive referrals, the RA will maintain an Excel spreadsheet with area providers, available services, payment options, and contact information. Before the end of the telehealth session, the Coach will also confirm the next scheduled telehealth session with the participant. Overall, the telehealth sessions with MI and coaching support are expected to last up to 30 minutes. In addition to the Coach-initiated telehealth sessions, participants will be encouraged by the Coach to request additional telehealth sessions as needed. Participants will send a text message to the RA requesting a video call. The RA will reply via text message with scheduling options, based on availability of the Coach. We anticipate that special requests for video calls will be a response to a pressing issue that is weighing on the participant, so these calls will occur within the same day as the request whenever possible. The T-CAP research procedures for RA and Coach will be monitored with a monthly Procedural Fidelity Checklist (included in the Appendix).

Telehealth app data collection. There are two types of data from the T-CAP app: (1) function data (e.g., frequency of messaging, date/time of video calls and duration of calls), and (2) two telehealth satisfaction questions completed by participants at the end of each telehealth session (see appendix). Both data types will be available for download (from the cloud) to TCU Box. The data will be identified by the phone number. The phone number will be replaced with the Research ID by the Project Coordinator, so that no identifying information will be included in the analytic dataset.

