Completed Provider Data Request Forms will be uploaded by the provider to TCU Box and available for download by authorized project staff. Data from the forms will be entered into a provider data tracking Microsoft Excel file at the IBR and maintained on a secure server at the IBR office.

14. Data Analyses: Describe how you will analyze your data to answer the study question

Aim 1: Demonstrate intervention feasibility by measuring study participant receptivity and utilization of the telehealth approach. Feasibility will be primarily assessed by descriptive analyses of participation, satisfaction, and telehealth usability data. We will examine distributions on these measures as well as characteristics of participants with high and low participation sample size, we will be more interested in trends than in statistical significance. Receptivity and utilization will be assessed by self-report measures as well as participation data from the T-CAP app. Self-report measures will include the Telehealth Usability Questionnaire (TUQ), Telehealth Session surveys, and semi-structured closeout interviews. The TUQ gauges constructs that are consistent with those in the telehealth literature and include: Usefulness, Ease of Use Interaction Quality, Satisfaction and Future Use, Interface Quality; and Reliability. TUQ scores of 4.0 (agree) and above on each domain indicate high receptivity. Scores below 4.0 will be interpreted as an indication that the participant encountered some challenge in that area of using the telehealth system. Data from the TCAP app will provide evidence of utilization (i.e., process data on session completion, duration, and number of unscheduled contacts). Two satisfaction questions are asked after each video conferencing session. We will primarily examine counts and distributions of these data but will also examine characteristics of participants with high and low levels of participation. All individuals will be invited to participate in an interview with a member of the research team. Our goal is to obtain feedback at the study closeout (Time 3) from a minimum of 6-8 participants. Drawing on our extensive qualitative experience, a semi-structured interview with questions from the TUQ, paired with relevant probes, will guide the interview to help us gain a better understanding about how the telehealth experience impacted participants.

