Aim 2: Evaluate the proposed T-CAP measures to assess their performance in gauging the impact of telehealth on initiation of in-person Substance Use (SU) treatment, short-term retention in referred SU treatment, and access to other appropriate treatment services (e.g., MAT). Our multidimensional approach includes data from self-report attendance and treatment engagement, self-report drug use, Coaches' advocate records on number of completed assertive referrals, and agency records from police and BH providers (including intake and during-program UA test results). In order to examine groups differences for intervention completers (C) vs non-completers (NC) (i.e., individuals who do not complete the 7 coaching video calls), group differences using t-tests and chi-square tests and we will estimate effect sizes needed for determining a sample size for a future R01 proposal. To assess potential assignment bias, we will test to see if there are baseline differences in demographics: participant race, gender, age and other demographic characteristics, as well as baseline measures of opioid use frequency and amount will be examined using chi-square and t-tests. Effect sizes will be computed for group differences on multiple outcomes (treatment initiation, retention, referrals to expanded SU service options, missed appointments). Service attendance records will be corroborated monthly with service provider records. Examinations of referrals to MAT and alternative pain management care between the C and NC groups, utilizing agency records data and the Coach tracking, will be conducted using a z-score to test differences in proportions of referral types. This will be calculated for all assertive referrals (resulting in scheduled appointments) collectively for a participant, as well as for different types of services.

Analyses of Secondary outcomes. We will examine differences between C and NC groups on several secondary outcomes. Analyses will typically involve t-tests, chi-square tests, and correlations. For example, we will use t-tests to assess differences between groups on the 3-month follow-up measures

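### Aim 2 compares all 7 calls with anything fewer and plans no analysis by number of calls taken; adding one is a cheap improvement.

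*Combined protocol and SAP*

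**What the plan says.** Section 11 sets the sample at 40 in a single group; participants "will be enrolled for the T-CAP study and all will receive the T-CAP intervention". Under T-CAP Intervention in the Study Procedures, "The 12-week telehealth intervention features 7 video calls on a smart phone". Scheduled Telehealth Sessions gives the timing as "1 telehealth MI each week for the first four weeks, MI 5 in week 6, MI 6 in week 8", with the seventh in week 12. Participants may also have unscheduled calls: "participants will be encouraged by the Coach to request additional telehealth sessions as needed".

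Section 14, Aim 2 compares completers with non-completers, the latter being "individuals who do not complete the 7 coaching video calls". Every between-group comparison named there uses this split: the t-tests and chi-square tests, the effect sizes for initiation, retention, referrals and missed appointments, and the z-test on referral proportions. The secondary outcomes and the comparison of self-report and urinalysis results use the same two groups.

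Finer exposure data appear only under Aim 1, where the app supplies "process data on session completion, duration, and number of unscheduled contacts". These are to be shown as counts and distributions, and the team "will also examine characteristics of participants with high and low levels of participation". That describes who participates much or little. It does not relate participation to Aim 2 outcomes.

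**The concern.** Call exposure can take eight values, 0 to 7, and Aim 2 reduces them to two by cutting at the top. Six of the seven calls fall by week 8, and the last follows four weeks later ("MI 5 in week 6, MI 6 in week 8, and MI 7 in week 12"). Someone who misses only that call has had 6/7 = 86% of the planned calls, yet is analysed with people who never accepted one.

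If outcomes improve steadily with calls taken, the two-group comparison dilutes that relation. The team planning the R01 would then have no description of how outcomes vary across levels of participation, although the data to produce it will be in hand.

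**Working it through.** **Is graded exposure used anywhere in Aim 2?** No. Each named comparison is completers against non-completers. Correlations are listed among the methods for secondary outcomes, but under a paragraph framed as that same contrast and with no exposure variable named.

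**Is there a plan figure to reproduce?** No. The documents give no attendance rate, power, alpha or assumed effect. The schedule adds up: 4 + 1 + 1 + 1 = 7 calls.

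**How much does the split lose?** Let X be calls completed (mean m, variance v) and P = Pr(X = 7). If the outcome is linear in X, the 7/7 indicator keeps the share

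r² = (7 − m)² P / [v (1 − P)]

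of the explained variance. All attendance inputs below are assumptions.

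*Independent attendance with probability p per call:* P = p⁷, m = 7p, v = 7p(1 − p). Here r² reduces to 7p⁶(1 − p)/(1 − p⁷), which is also the share of non-completers who took exactly 6 calls. For p = 0.80: P = 0.210, so r² = 0.367/0.790 = 0.46.

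*Attendance varying between people (beta-binomial, mean μ, concentration c):* m = 7μ, v = 7μ(1 − μ)(c + 7)/(c + 1). For μ = 0.5, c = 2, all eight values are equally likely: P = 0.125, m = 3.5, v = 5.25, so r² = (12.25 × 0.125)/(5.25 × 0.875) = 0.33.

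| Assumed attendance | Expected completers of 40 | Mean calls, non-completers | Non-completers with 5 or 6 | Share kept (r²) |
|---|---|---|---|---|
| Independent, 0.95 | 27.9 | 5.8 | 99% | 85% |
| Independent, 0.90 | 19.1 | 5.7 | 95% | 71% |
| Independent, 0.80 | 8.4 | 5.2 | 81% | 46% |
| Independent, 0.70 | 3.3 | 4.7 | 61% | 27% |
| Varying, mean 0.8, c = 2 | 19.2 | 4.3 | 56% | 54% |
| Varying, mean 0.8, c = 5 | 14.5 | 4.8 | 67% | 50% |
| Varying, mean 0.7, c = 3 | 10.5 | 4.2 | 50% | 43% |
| Varying, mean 0.6, c = 2 | 8.2 | 3.5 | 37% | 40% |
| Varying, mean 0.5, c = 2 | 5.0 | 3.0 | 29% | 33% |
| Varying, mean 0.5, c = 0.5 | 12.1 | 2.0 | 21% | 61% |

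The range is 27% to 85%. Independent attendance at 0.6 or 0.5 would give 13% or 5.5%, but with only 1.1 or 0.3 expected completers there would hardly be a group to compare.

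**What this means for power.** A simulation with N = 40, two-sided 0.05, a linear correlation of 0.4 between calls and outcome, and six assumed call distributions (6,000 runs each) gave about 73–76% power when the count was analysed and 26–52% for the split. With a correlation of 0.5 the figures were 91–93% and 39–73%. These illustrate the loss; they are not predictions for this study.

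**The case against.** A case can be made for leaving Aim 2 alone, and parts of it stand.

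- **Taking 7 of 7 as completion is an ordinary definition.** The sessions follow a script, and session 7 has its own closing role: a plan for continuing recovery. This stands. A reader might infer that the cut is arbitrary; the documents do not support that, though they also do not link session 7 to an adequate dose.
- **The make-up of the non-completer group is unknown.** A reader might infer that it will consist mainly of people who took nearly all the calls. That needs good attendance, which the documents neither state nor imply. In the table, the share with 5 or 6 calls runs from 21% to 99%. Early dropout is as compatible with the plan as near-completion.
- **The loss may be small.** At independent attendance of 0.95 the split keeps 85%, and under a threshold at 7 it keeps everything. This stands as a limit on the size.
- **Aim 2 wants group-difference effect sizes.** A rank correlation does not supply these, so replacing the main contrast is not warranted. Nor is a table by 0, 1–3, 4–6 and 7 calls: at independent attendance of 0.80 to 0.95, only about 0 to 1.3 of 40 people are expected to take 3 calls or fewer.
- **Call count is as self-selected as completion.** This stands. A reader might hope that a count analysis would show how many calls are needed; in a single-arm study it cannot.
- **Trends matter more than significance in a feasibility study.** That remark is made under Aim 1, and a trend across 0 to 7 calls is what the two-group split cannot display.

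**Conclusion.** The gap is real but modest. As written, Aim 2 pools 0 to 6 calls and contains no analysis of outcome by number of calls, while the data for one are collected under Aim 1. The 27% to 85% retained rests on assumed attendance patterns and a linear relation; the documents fix neither. This is a cheap improvement to the analysis plan. It is not a flaw that invalidates the planned contrast, and it gives no reason to drop it.

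**What to change.** Keep the completer versus non-completer comparison and its effect sizes. Add to Section 14, Aim 2 a prespecified analysis of each outcome (initiation, retention, referrals, missed appointments, drug use) against the number of the seven scheduled calls completed, from 0 to 7. Take the count from the app log, checked against the Coaches' session records, and exclude calls that participants requested in addition. Use rank correlation or regression, and report the estimate with a confidence interval and a plot.

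State that the result is an association only: participants choose how many calls to take, and reaching the later calls depends on staying engaged over the same weeks in which retention is measured.

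The cost is a few lines of wording and a little more analysis, with no new data, visits or participant burden. The trend analysis assumes a roughly monotone relation, which the plot lets the reader judge.

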(T-CAP), a technology-based intervention **development** and **feasibility** R21 study to examine the impact of integrating clinical telehealth services within an existing Illinois (IL) police Opioid Diversion Program (ODP). The study includes three key components: 1) Development and testing of the proposed multidisciplinary telehealth intervention integrated within a state-supported police diversion program; 2) use of telehealth technology to provide ODP participants with access to clinically qualified staff (referred to as the Coach); and 3) expanding and strengthening the available service infrastructure including pain management alternatives to the use of potentially addictive medications and by having the Coach reach out to new and underutilized providers in local communities (e.g., underutilized physicians and other medical providers such as certified nurse practitioners). Modifications target use of virtual consenting and utilizing FedEx mail to issue study cell phones to participants, replacing in-person meetings with the T-CAP research assistant. No modifications have been made to the T-CAP telehealth intervention and **no in-person interactions will occur as a part of this study**. 10.28.2022 modification will include the removal of the randomization procedure; specifically, no one will be assigned to what was previously referred to as the "Treatment as Usual" condition. All participants will receive the T-CAP telehealth intervention.

The specific aims for the proposed research are as follows: (Aim 1) Demonstrate intervention feasibility by measuring study participant receptivity and utilization of the telehealth approach, and (Aim 2) Evaluate the proposed T-CAP measures to assess their performance in gauging the impact of telehealth on initiation of in-person Substance Use (SU) treatment, short-term retention in referred SU treatment, and access to other appropriate treatment services.

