Individual interviews. A member of the research team will coordinate interview scheduling with the RA, who in turn will text message virtual meeting options to the participant. The scheduled meeting will be confirmed by the RA with both parties. The semi-structured interview with a member of the research team will take via meeting-specific HIPAA compliant Zoom chat or by phone. Audio recordings will be processed at the IBR.

Participants will be advised that all identifying information will be removed from the transcribed interview and no identifying information will be reported for the project.

Interviews are expected to take 30 minutes to complete and participants will receive an electronic gift card (\$20) for their participation. Participants who are interested will receive a Qualtrics link for the Participant Interview Consent and Media Release documents.

Responses will be recorded via Qualtrics where participants will click on their responses such as "I agree to participate" or "I do not agree to participate." Audio files will be transcribed for qualitative analysis. Agency Records. Behavioral healthcare data will be obtained for participants in both conditions.

Participants will authorize the release of these data to the research team by signing the *Primary Study Informed Consent* at the start of the study. As part of the data-sharing piece, the research team will also obtain a Memorandum of Understanding (MOU), signed by the behavioral provider and the T-CAP PI. To request treatment data, the IBR research staff will send via email, monthly requests to providers with an attached Provider Data Request Form (included in the Appendix) for each participant receiving services at their agency. The form will include only a unique identification number (i.e., Treatment Code) which the provider will use to identify the participant. No participant name will appear on the form or in the email.

The form has space for the provider to include the following information items:

- Primary diagnosis
- Level of care (outpatient, intensive outpatient, residential, detox)
- Length of program (number of weeks)
- Treatment initiation date
- Number of sessions scheduled this month
- Number of missed sessions this month
- Drug test results for this month
- Treatment discharge date

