of treatment motivation and psychosocial function from the TCU Client Evaluation of Self and Treatment (TCU CEST), a widely used form listed on the IBR web page. Validation of recent (last few days) self-reported opioid use will be compared with drug testing outcomes at each assessment time point using McNemar's test for change of state, as well as computing sensitivity and specificity statistics and the kappa statistic as a measure of agreement. We will compare self-report, as well as urinalysis (UA) results from agency drug screens between the two groups.

15. Potential Risks and Precautions to Reduce Risk: Indicate any physical, psychological, social, or privacy risk which the subject may incur. Risk(s) must be specified. Also describe what measures have been or will be taken to prevent and minimize each of the risks identified. If any deception is to be used, describe it in detail and the plans for debriefing.

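### The effect sizes meant to size the R01 come from completers versus non-completers of the seven calls, a contrast that does not estimate the effect of T-CAP

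*Combined protocol and SAP*

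**What the plan says.** The opening study description (before Section 10) records that the modification of 10.28.2022 removes randomisation and the usual-care condition: "All participants will receive the T-CAP telehealth intervention". It also says that findings will inform an R01 containing a multi-site randomised trial of T-CAP.

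Section 14, Aim 2 defines its groups as "intervention completers (C) vs non-completers (NC) (i.e., individuals who do not complete the 7 coaching video calls", compares them by t-test and chi-square, and in the same sentence states that "we will estimate effect sizes needed for determining a sample size for a future R01 proposal". The outcomes are listed: "Effect sizes will be computed for group differences on multiple outcomes (treatment initiation, retention, referrals to expanded SU service options, missed appointments". Referral proportions are compared between the same groups, and "This will be calculated for all assertive referrals (resulting in scheduled appointments) collectively for a participant". The secondary analyses reuse the split: "We will compare self-report, as well as urinalysis (UA) results from agency drug screens between the two groups".

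The only check on comparability is this: "To assess potential assignment bias, we will test to see if there are baseline differences in demographics", together with baseline opioid use. No adjustment follows from it.

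Under Study Procedures, Scheduled Telehealth Sessions puts the calls in weeks 1, 2, 3, 4, 6, 8 and 12, and has the Coach arrange referrals as part of those sessions. Agency Records still reads: "Behavioral healthcare data will be obtained for participants in both conditions".

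**The concern.** The R01 would compare people randomised to T-CAP with people randomised to something else. Here both groups are offered T-CAP, and they differ in whether they went on to attend every call; someone who attends six of seven counts as a non-completer. Membership cannot be known at baseline, and nobody can be a completer before call 7 in week 12.

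The outcomes accrue over those same weeks. A participant who leaves treatment may stop taking calls, so poor retention can cause non-completion as well as the reverse. Referrals are partly mechanical: fewer sessions mean fewer occasions for the Coach to arrange one.

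At stake is the sample size of the next trial. An effect size from this contrast can be far from the quantity the R01 needs, and nothing in the plan would reveal by how much or in which direction.

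**Working it through.** **No stated figure to reproduce.** The sample of 40 is given without alpha, power, effect size, completion rate or event rates. Every outcome, attendance, alpha and power input below is therefore an assumption. Only the call weeks and the total of 40 come from the protocol.

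**Step 1. What the contrast estimates.** Let Y0 be a participant's outcome without T-CAP, and suppose T-CAP adds the same amount δ for everyone. Then

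mean(Y | C) − mean(Y | NC) = [mean(Y0 | C) + δ] − [mean(Y0 | NC) + δ] = mean(Y0 | C) − mean(Y0 | NC).

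The effect δ cancels and only selection is left. With no selection the contrast is zero although T-CAP helps everyone equally. With selection it is non-zero although T-CAP does nothing.

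**Step 2. How large it can be when T-CAP does nothing.** Assume 50%, 60% or 70% are retained to week 12; dropout week is uniform over weeks 1 to 12; each call is attended with probability 0.9 while in treatment and probability a from the dropout week on; and everyone is planned to stay to week 12.

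- Retained participants complete all seven calls with probability 0.9^7 = 0.478.
- For dropout in weeks 1 to 12, the calls still to come number 7, 6, 5, 4, 3, 3, 2, 2, 1, 1, 1, 1. The completion probability of dropouts, q, is the average of 0.9^(7−k) × a^k over these k.
- Example with a = 0.7 and 60% retained: q = 0.251. Completers are 0.6 × 0.478 + 0.4 × 0.251 = 0.388 of the sample. Retention is 0.287/0.388 = 0.741 in completers and 0.6 × 0.522/0.612 = 0.511 in non-completers, a gap of 23 points.

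| Attendance after dropout (a) | Gap in retention, C minus NC (70% to 50% retained) |
|---|---|
| 0.9 | 0 points |
| 0.85 | 6 to 7 points |
| 0.7 | 20 to 25 points |
| 0.5 | 31 to 40 points |

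A different model agrees for a continuous outcome. One latent trait drives both completion and outcome, T-CAP has no effect, and completion is 30% to 70%. Correlations of the trait with completion and outcome of 0.3/0.3, 0.5/0.5 and 0.7/0.5 give d of 0.14 to 0.15, 0.41 to 0.42 and 0.58 to 0.60.

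**Step 3. Consequence for an R01.** Take d = 0.5, which lies inside that range. At 80% power and two-sided 5%, the normal formula gives 2 × (1.960 + 0.842)² / 0.5² = 62.8, or 63 per arm; the t-test version gives 64. With 64 per arm the noncentrality is d × √32. A true effect of 0.2 gives 1.13 and power 20%; a true effect of 0.3 gives 1.70 and power 39%.

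**Step 4. The baseline tests.** For a true baseline difference of 0.5 SD among 40 people, the noncentrality is 0.5/√(1/n1 + 1/n2). A split of 8/32 gives 1.26 and power 23%; a split of 20/20 gives 1.58 and power 34%. A non-significant result would say little about comparability.

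**Step 5. What a single arm can supply.** With all 40 analysed, a proportion near 50% has a half-width of 1.96 × √(0.25/40) = 15.5 points, and the 95% limits for an SD, √(39/χ²), are 0.82 to 1.28 times the estimate. With 32 analysed these become 17.3 points and 0.80 to 1.33.

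**The case against.** The best defence is that this is a feasibility R21 and that Aim 2 is worded as evaluating how the measures perform. Describing completers against non-completers serves that purpose, and nothing here argues against it. The defence fails only for the sizing use, which Aim 2 states outright. The remark that trends matter more than significance belongs to Aim 1 and does not cover it.

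Several stronger readings are tempting but unsupported:

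- *Group membership is unknown until week 12.* True of completers only. A participant who withdraws early is a known non-completer before then.
- *The contrast must exaggerate the benefit.* The documents give no attendance or outcome figures, so neither the direction nor the size of the error is fixed.
- *The baseline tests are beside the point because all selection is post-baseline.* Part of it, such as motivation, may exist at baseline. The tests fail because nobody is assigned, power is low, no adjustment is planned, and they cannot reach dropout after baseline.
- *Lost phones and rescheduling create non-completers.* The plan provides a replacement phone and has the research assistant handle schedule changes.
- *The plan offers this contrast as its evidence of efficacy.* The opening description expects preliminary evidence of efficacy but does not tie it to completers versus non-completers.
- *The absent control-arm rate is a further error of this contrast.* Any single-arm study lacks one. The plan needs only to say where it will come from.

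**Conclusion.** The point holds. With one arm, a randomised R01 in view and no other source named, Aim 2 assigns to the completer contrast a quantity that it cannot give. That conclusion rests on the design and the text, not on the simulated figures. The gap of 0 to 40 points and the power of 20% to 39% show what is possible under stated assumptions; they do not predict this study's result.

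Participants and the descriptive Aim 1 are unaffected. The damage would fall on the later application, so this is a correction that should be made rather than a bar to proceeding.

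**What to change.** In Section 14, Aim 2:

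1. Remove the use of completer versus non-completer effect sizes for sizing the R01, and label the comparison, including its secondary outcomes, as a description of engagement only.
2. Take from this study single-arm planning quantities: outcome proportions, SDs, attrition and call completion. Report each with a 95% confidence interval and the number analysed, in all enrolled participants who meet the recent-use condition that Section 11 sets for the primary analyses.
3. State that the R01's control-arm rate and target difference will be justified from another source.
4. Reconcile the reference to two conditions under Agency Records, and the assignment-bias wording in Aim 2, with the single-arm design.

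No new data are needed. The cost is that the pilot yields no headline between-group effect size, and the team must find and defend a control rate and a target difference when it writes the application.
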